To account for differences in the frequency of participant contact between the two study groups, blinded measurement staff will systematically assess for AEs in both the intervention and control groups through use of a standardized questionnaire (see MOP) that is administered at each major assessment time point. If any items are endorsed on the questionnaire, the blinded measurement staff will gather additional information and, if necessary, follow the steps for recording and reporting adverse events outlined below and in section **IX.E**. AEs uncovered in the course of treatment will also be subject to the procedures below. Combining between visit and at visit AEs will result in an alternative count that the DSMB requested. This alternative count will be comprised of all AEs, whether reported at or between visits. Blinded coaches will be unaware if an AE was reported between visits, and any duplicates will be removed by an unblinded reviewer (*DSMB Approval, 12.16.2020*)

All AEs, including those not meeting the criteria for SAEs, will be captured on an Adverse Event Form or Serious Adverse Event Form (see **Appendix D**), which must be approved of and signed by the clinical site PI. Information to be collected includes event description, time of onset (and offset if applicable), assessment of severity, relationship to study treatment, expectedness, actions taken,

and outcome of the event. Additionally, all SAEs will require categorization (e.g., death, hospitalization, permanent impairment, etc.) and documentation of any interventions implemented in response to the event.

All AEs occurring during a participant's study participation must be documented appropriately regardless of relationship. All AEs will be followed by the DSMB to adequate resolution and will be recorded in the data collection system. Any medical condition that is present at the time that the participant is screened will be considered as baseline and not reported as an AE. However, if the study participant's condition deteriorates at any time during the study, it will be recorded as an AE. Changes in the severity of an AE will be documented to allow for an assessment of the duration of the event at each level of severity. AEs characterized as intermittent require documentation of onset and duration of each episode.

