Adverse event questionnaires and reporting forms are included in Appendix D of the study protocol. Once a site's research staff becomes aware of an adverse event's occurrence, that staff (i.e., PLAN coach or assessor) will consult with the clinical site PI or project coordinator to complete the appropriate event form and notify the SMC. Adverse event questionnaires will only be administered after assessment measurement by blinded measurement staff, who will correspondingly complete an adverse event log (10.12.20; *DSMB approval, 12.16.2020*). The SMC will then evaluate the severity of the event and determine the necessity for immediate action on behalf of the study group. If immediate action is necessary, the SMC will consult with the Steering Committee to recommend a course of action (e.g., discontinuation of treatment, referral to higher level care). If immediate action is not necessary, the event will be documented in the study database and discussed at the next scheduled DSMB meeting. Additionally, the DCC will prepare monthly reports that summarize adverse events and assess whether there is evidence of a between group difference in AE and SAE rates.

All adverse events and study withdrawals, together with a detailed explanation of the event and withdrawal, will be forwarded to the DCC and the DSMB. In addition, at its regular meeting, the DSMB will summarize all adverse events of any severity, to be forwarded to the IRB via the designated PI. All serious adverse events will be immediately recorded by the clinical site PI and reported to the IRB and DCC, via the designated PI; information (i.e., event, actions, and implications for study) will then be distributed to the other clinical sites. Any SAEs and AEs that are judged to be possibly or probably related to participation in the study and/or change their assessment of risk of participation will be immediately reported to the DSMB. The remaining SAE/AEs will be sent to the DSMB with the 6 month reports (***DSMB approved protocol addenda, 3.18.19***). If any participant appears to be in crisis but the event is not classified as an SAE, appropriate action will be taken based on established suicide and crisis protocols, and any adverse event will be reported promptly to the DSMB and IRB.

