5. *Once the measurement has stopped fluctuating, the coach will record the weight on a hard copy of the "Height and Weight" REDCap form that s/he will print off prior to the appointment.*
6. *The coach will repeat this procedure a second time.*
7. *The coach will instruct the participant to step off the scale.*
8. *The coach should wipe down the scale pre and post measurement with a Lysol wipe if the participant is bare footed.*

MANUAL CALIBRATION OF THE SCALE

1. *All PLAN coaches will use Pro-Form 15-pound kettle bells to calibrate their scales.*
 - a. *A staff member from the University at Buffalo will perform weight measurements with all Pro-Form kettle bells on a calibrated scale.*
 - b. *The staff member will document the exact weight of each kettle bell.*
 - c. *The staff member will write the exact weight on a piece of painter's tape and tape it to the kettle bell.*
 - d. *The staff member will mail out the kettle bells each site.*
2. *All PLAN coaches will take weight measurements with their kettle bells each time their scale is used.*
 - a. *The scale should always measure the known weight of the kettle bell that was documented by the University at Buffalo on the painter's tape.*
 - b. *If the scale measures the weight of the kettle bell as something different than the known weight, the coach will document the discrepancy. The coach will then make arrangements to send the scale to SR Scales for re-calibration.*

WEIGHT MEASUREMENT REPORT

1. *For analysis of outcome measures (see 11 in Weight Procedures above; (This change was made on 9.18.17 prior to review and approval by the DSMB, DSMB approved protocol addenda on 11.2.18).*

Use of Weight App was discontinued (DSMB approved change, 11.18.19). Hard copy height and weight measurement forms will be uploaded to the secure REDCap database to allow the CCC, DCC and TFC to check for transcription and/or unit of measurement errors.

Remote assessments Protocol

Step 1: Coach Instructions for CONTACTING FAMILY

1. Schedule phone call with family to introduce the remote assessment, check for materials, review instructions, describe changes in payment, complete the AE survey, and to schedule an assessment date with a blinded measurement coach. *A random subset of families from each site will be asked to complete the height protocol for a second quality control measure of this remote height measurement.*

- a. See email script if they do not answer the phone:

"Hello [Parent],

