a. “We will mail a standardized scale and [item(s)] to your address for the assessment. Please confirm your mailing address and any special delivery instructions for your residence.”

2. Contact PC to coordinate delivery of materials

f. Schedule the family’s remote measurement

i. “To allow time for materials to arrive for the measurement, we will schedule 2 weeks out from this call.”

ii. Give 2-3 possible days/times to schedule appointment.

g. Complete AE survey according to protocol

i. “At this time I have a 5-10 minute survey to go through with you. Is now a good time to complete this?”

1. If yes, complete AE survey.
2. If no, “is there a convenient day/time where I can contact you to complete this survey?” or email it to the family

h. Notify family that necessary questionnaires will be emailed and should be completed before the measurement appointment through REDCap.

i. If family does not have computer/phone access with internet:

1. Surveys can be done over the phone BEFORE the appointment
 - a. AEQ, DDs, FNPA, 24M Parent/Child
2. Measurement instructions will be mailed to their address

ii. Send reminder email 1 day before assessment if questionnaires are not complete

- i. Check when family's next well child visit is to coordinate in person follow-up measurement at a convenient date and time
 - i. "In addition to the remote measurement, we will also schedule a follow-up measurement at the pediatric office. Does your child have an existing well-visit appointment that would be convenient for you to schedule this follow-up?"
 - ii. If not, schedule a follow-up appointment that will take place in the summer
- j. Ending the phone call
 - i. "Thank you so much for your time today, I will send you a 1 week and 1 day reminder prior to your assessment. Please contact me with any changes or questions in the meantime."
- 2. Record all assessment information into your site's specific tracking spreadsheet.
 - a. Add date and time, and all other necessary information, (UB Assessments - Tracking, WU, NCH, UR)
 - b. Include family's consent for audio/video recording
- 3. Contact a blinded measurement coach to run the assessment via video conference or phone.
 - a. For 24 month assessments, both the blinded assessor and the PLAN Coach should be present
- 4. Send video conference email link to family and assessor using <https://zoom.us/home?zcid=2478> or Webex
 - a. Set the duration as 30 min, or 60 min for a 24 month assessment.
 - b. Set a password.

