 - c. Attach Family Instructions for measurements
- 5. Email all the surveys to the family through REDCap (see next section)
- 6. Confirm assessment dates with family one week before and the day of the assessment
 - a. Include the call-in information and instruction sheet again.

Step 2: PLAN Coach Instructions for FORMS AND PAPERWORK COMPLETION

NOTE: For 6, 12, and 18 month assessments, all surveys should be completed by families BEFORE the assessment.

For 24 month assessments, surveys should be completed by families BEFORE the assessment, AND the PLAN Coach should attend the assessment to give FBT materials and finish payment AFTER the blinded assessor leaves the call.

- 1. For families doing 12- and 24-month assessments, have them complete the online questionnaires.
 - a. At 12 month assessments: Child DD Validation, Child DD, Parent DD.
 - b. At 24 month assessments: Child DD Validation, Child DD, Parent DD, FN & PA, and 24 Month for both Child and Parent.
 - c. For families with internet access, use REDCap to send the online surveys.

- i. In the family's REDCap record, click the circle that corresponds to the questionnaire that needs to be sent
 - ii. Under the "Survey Options" drop down menu, select "Compose Survey Invitation"
 - iii. Fill out the invitation form
 1. Send out immediately
 2. Check the box to enable reminders and choose to resend every 3 days with recurrence up to 5 times
 3. Make sure it is your email address the email will be from, and choose the participant's email address to where it will be sent
 4. Type in subject line: "PLAN with Families 12/24 month survey"
 5. Compose a message in the text box.
 - a. For example, "Hi [Name], Please click the link and complete the questionnaire, following the directions provided. If you have any questions, contact your PLAN coach at [phone number here]."
 - b. Be sure to clarify if that specific questionnaire needs to be filled out by the parent or the child
 - iv. Repeat for each questionnaire that needs to be completed
- d. For families who don't have access to internet
 - i. DD tasks, FNPA, and 24 Month Surveys can be done over the phone BEFORE the assessment
 - ii. Contact PC about mailing paper forms if necessary

2. If the family needs a re-assent, re-consent, or an addendum:
 - a. These will become forms in REDCap
 - b. You will send them just like you send the surveys BEFORE the assessment
 - c. In the subject line, use: "PLAN with Families Consent form for [Name of participant]"

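### The remote-visit script runs the adverse event survey before measurement, against the blinded, after-measurement rule; separately, no planned analysis uses measurement mode

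*Combined protocol and SAP*

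**What the plan says.** **AE collection.** Adverse Event Reporting Procedures, in a sentence dated 12 October 2020 with DSMB approval on 16 December 2020, states: "Adverse event questionnaires will only be administered after assessment measurement by blinded measurement staff". Adverse Event Assessment and Tracking gives the reason, which is unequal contact between the arms, and says "blinded measurement staff will systematically assess for AEs in both the intervention and control groups". Masking of Assessment Staff also assigns AE data collection to blinded coaches.

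**The remote script** (Remote assessments Protocol, Appendix C). Step 1 describes the contacting coach's call as the occasion to, among other things, "complete the AE survey, and to schedule an assessment date with a blinded measurement coach".

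- Item f: "To allow time for materials to arrive for the measurement, we will schedule 2 weeks out from this call".
- Item g: "At this time I have a 5-10 minute survey to go through with you. Is now a good time to complete this". If the moment is inconvenient, the survey is rescheduled or emailed.
- Item h, for families without internet, lists these as phone surveys to be done before the appointment: "AEQ, DDs, FNPA, 24M Parent/Child".
- The next numbered instruction, item 3: "Contact a blinded measurement coach to run the assessment via video conference or phone".
- Step 2 adds: "For 6, 12, and 18 month assessments, all surveys should be completed by families BEFORE the assessment". It does not name the AE questionnaire.

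**The 24-month outcome.** SAP III.B.7, item 1, takes any available 24-month value with no further handling. The family height instructions have an enrolled parent or guardian measure the child, and Masking Procedures concedes that families cannot be masked. Section E lists five sensitivity analyses, none of which concerns mode. The script also plans an in-person follow-up measurement (Step 1, item i) and a repeat of the remote height in a random subset. The plan gives no analysis of either.

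**The concern.** The blinded questionnaire exists because FBT families see staff more often and so have more chances to report events. The DCC compares AE and SAE rates between groups every month. If a treating coach asks the questions, the masked count is no longer masked.

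The early timing also leaves a hole. The AE form asks about the period since the last major assessment. An event between the call and the visit falls after this form is completed and, read literally, before the period covered by the next. At 24 months there is no next form.

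Mode of measurement is a separate and smaller matter. Remote heights come from unmasked parents, and mode appears in no planned output. A reader of the results could not tell whether remote share, or the effect of mode, was similar in the two arms.

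**Working it through.** **1. The AE passages side by side**

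| | AE rule and masking sections | Remote script |
|---|---|---|
| When | After measurement | On the scheduling call, with measurement booked 2 weeks later; by phone before the appointment if no internet |
| Who | Blinded measurement staff | The coach who contacts the family |

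The timing conflict is explicit. That the caller is unblinded is an inference, but a strong one: the caller must then contact a separate blinded measurement coach, and at 24 months the script has the blinded assessor and the PLAN coach both attend as different people. Item g refers back to the protocol, but its scripted words run the survey on the call.

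Maximum gap: 14 days out of a 6-month recall period, 14/182.6 = 7.7%. It is a maximum because the survey may be rescheduled or emailed.

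**2. Questionnaires and visits affected (upper bounds)**

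Inputs: the planned accrual table (56, 84, 84, 84, 84, 82, 54; total 528), spread evenly within quarters, starting 1 November 2017 and ending 31 May 2019. The alternative is even accrual from 1 November 2017 to 15 August 2019, the closing date in the Randomization section. Scheduled questionnaires: 4 x 528 = 2112. The documents give no start date for remote visits, so 1 March to 19 May 2020 is assumed; 19 May is the IRB approval of the coronavirus addendum.

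Target dates after each cut (no 6-month target falls after any of them):

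| Cut | 12 + 18 + 24 months, planned table | Share of 2112 | Even accrual |
|---|---|---|---|
| 1 Mar 2020 | 82 + 247 + 417 = 746 | 35% | 40% |
| 19 May 2020 | 12 + 175 + 344 = about 530 | 25% | 31% |
| 12 Oct 2020 (rule dated) | 0 + 44 + 210 = 254 | 12% | 17% |
| 16 Dec 2020 (DSMB approval) | 0 + 0 + 151 = 151 | 7% | 12% |

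24-month targets alone: 417/528 = 79% and 344/528 = 65% after the first two cuts (82% and 70% with even accrual). All are upper bounds on remote visits, because no end date for remote assessment is given.

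**3. What a height error would do (illustration)**

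For height h, error d and percent over BMI p, the outcome moves by (100 + p) x ((h/(h - d))^2 - 1). With assumed h = 140 cm and p = 50, this is 2.17 points at d = 1 cm and 0.64 at 0.3 cm. Over 130-150 cm, p of 30-80 and either direction of error, 1 cm gives 1.7-2.8.

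- Equal error with equal remote shares largely cancels between arms.
- A 1 cm error in one arm only, at 65-79% remote, would shift the difference by 0.65 x 2.17 = 1.4 to 0.79 x 2.17 = 1.7 points. At 0.3 cm the shift is 0.4-0.5. The smallest planned effect is 5.3.

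The one-arm error is an assumption.

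**4. Precision of an in-person-only run**

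SE = SD x sqrt((1 + (m - 1) x ICC)/n + 1/n), with n = N/2, m = n/12 families per coach, SD 15.3, ICC 0.04 in FBT and 0 in UC. Power uses a noncentral t with 8 df (12 coaches less 4 sites), for a difference of 5.3.

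| Families | SE | 95% half-width | Power |
|---|---|---|---|
| 528 | 1.587 | 3.7 | 0.83 (SAP Table 1: 0.84) |
| 528 - 344 = 184 | 2.40 | 5.5 | 0.49 |
| 528 - 417 = 111 | 3.01 | 6.9 | 0.34 |

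Because 344 and 417 are upper bounds on remote visits, 184 and 111 are minimum in-person counts and these power figures are floors.

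**The case against.** **On the AE survey.** The after-measurement rule is later than the remote addendum (DSMB approval 7 May 2020), so this is probably a script that was not updated. That explains the conflict but does not remove it: both texts stand, and staff who follow the appendix would breach a DSMB-approved rule.

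Three stronger readings are tempting, and the documents do not support them.

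- *Only FBT sessions could pick up events in the gap.* Adverse Event Assessment and Tracking lets events surface through any participant contact, including scheduling calls and email. It also has events recorded until 7 days (non-serious) or 30 days (serious) after participation ends. UC families get reminders and the remote visit too. What is lost is systematic questionnaire coverage; FBT families simply have more of the other contacts.
- *A quarter to a third of questionnaires breach the timing rule.* The 25-35% counts from remote start, before that rule was written. It bears only on who administers the survey.
- *Masking of the primary outcome is broken.* The separate caller keeps the blinded assessor from hearing AE answers before measuring.

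**On mode.** In-person visits were halted generally and randomisation is blocked within clinic, so mode should follow calendar date more than arm. Safeguards exist: guidance from a blinded coach, a practice check on an object of known height, a 0.3 cm repeat rule, photographs where there is no webcam, and the random repeat. The SAP also plans outlier-robust analyses (III.B.8). All of this stands, and a reader should not infer that remote measurement biased the result. These steps still do not show whether mode or its effect differed by arm. The random repeat follows the remote protocol, so it tests repeatability, not agreement with in-person values.

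**Conclusion.** **AE survey: wrong as written, and should be corrected.** The script and the AE rule cannot both be followed. The consequence is modest: loss of masked collection where the script was used, and up to 14 days (at most 7.7% of a recall period) outside the systematic form before each remote visit, with no later form at 24 months. The upper bound on questionnaires affected is 12-17% for the timing rule from its date, or 7-12% from DSMB approval. For the question of who administers the survey it is 25-35% from remote start (31-40% with even accrual). The latter rests on the inference about the caller. All these shares rest on assumed accrual and, for the last, on an assumed remote start.

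**Mode: a cheap, supportive improvement, not an error.** Up to 65-79% of 24-month target dates (70-82% with even accrual) fall after remote start, and no planned analysis uses mode. Bias needs error or remote share to differ by arm, and the documents give no evidence of either.

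The contents page lists a COVID-19 assessment addendum whose text was not available for this check. The statistical section was available and contains no analysis by mode.

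**What to change.** **AE survey.** Reconcile Steps 1 and 2 of the Remote assessments Protocol with Adverse Event Reporting Procedures, Adverse Event Assessment and Tracking, and Masking of Assessment Staff, so that the blinded measurement coach gives the AE questionnaire after the remote measurement. Cost: wording, plus the survey's 5-10 minutes on that coach's call.

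**Mode.**

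1. Carry measurement mode into the analysis dataset and report it by arm.
2. Compare remote values with the in-person follow-up values already planned, within child and by arm, allowing for growth between the two dates. This is the most direct check on measurement.
3. Add one supportive run of the primary model by mode. Label it as confounded with calendar period; it cannot isolate measurement error.
4. State before unblinding which value counts as the 24-month value when a remote and an in-person value both exist.

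Cost: one data field, some SAP wording and a few extra runs. An in-person-only analysis would be imprecise (power of at least about 0.34-0.49 for 5.3 on the planned accrual table), so it can support the primary result but not replace it.

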The clinical site PIs will record all reportable events with start dates occurring any time after informed consent is obtained until 7 (for non-serious AEs) or 30 days (for SAEs) after the last day of study participation. Events will be followed by the DSMB for outcome information until resolution or stabilization.

It is important to note that in previous similar clinical trials in the PIs' respective laboratories, the procedures outlined above have been used to protect against and minimize potential risks to participants, and they have proved effective in preventing emotional and physical complaints as well as adverse events.

Due to the fluid situation of COVID-19, 3 additional questions have been added to the AE questionnaire. Asking these questions could give us data on the effects of the pandemic and could help explain changes in FBT attendance and assessment retention.

- i. Do you have a positive COVID-19 test?
- ii. Did you have exposure to someone with a known positive COVID-19 test?
- iii. Did you need to get tested for COVID-19?

(emergency status implemented 3.16.2020, DSMB approval, 5.7.2020)

Adverse Event Reporting Procedures

Upon initial receipt of information, all fatal or life-threatening suspected serious adverse events will be immediately reported to the IRB of Record, internal IRBs, NHLBI, SMC, and DCC via [name] and the clinical site PIs. All non-fatal, non-life-threatening suspected SAEs will be reported within 15 calendar days to the IRB of Record, internal IRBs, NHLBI, SMC, and DCC via [name] and the clinical site PIs. Any unanticipated problems that do not classify as SAEs will be reported within 14 days of the investigator becoming aware of the problem to the IRB of Record, internal IRBs, NHLBI, SMC, and DCC via [name] and the clinical site PIs. All UPs will also be reported within 30 days of the IRB's receipt of information to the Office for Human Research Protection via the IRB. Non-serious adverse events will be documented in the study database following their occurrence and will be reported annually to the IRB of Record and internal IRBs via [name] and the clinical site PIs. See Table 6 for a detailed outline of reporting timelines.

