In addition to the existing procedures referenced above, the SMC recommends that as soon as child mental health SAEs are reported, to a coach or a PLAN staff designee verbally informs the participants' primary care provider and/or pediatric office staff designee with the description of the SAE, date, and referral so that they may follow-up according to their office procedure. Specifically, if a child enrolled in the study reports self-injury, a suicide attempt, or harm to others, then this will be addressed as a SAE and reported verbally to the pediatrician. The event will be reported by the individual with the most amount of information within 24 business hours of learning about the event. If a medical, behavioral, or mental health intervention is **deemed necessary to address this event, it is the pediatrician's responsibility to follow up with their patient to ensure appropriate care is provided**. Before this procedure goes into effect, the PLAN coach will communicate this plan with each pediatric practice to develop a practice-specific protocol with who to contact and how. In the event that a coach is unsure about the severity of the child mental health AE, they will collaborate with the local-site PI to determine the severity of the event and whether or not it should be reported to the pediatric office. All other mental health AEs will not be reported to the pediatrician, but will be reported to the IRB and DSMB as part of normal reporting procedures (***DSMB approved protocol addenda, 11.18.19***).

If a parent becomes pregnant, the PLAN coach will notify the clinical site PI and all weight loss treatments will be stopped. The family's continuation in the study will be limited to the child, siblings and non-participating parent if enrolled. The DCC, DSMB, and IRBs will be notified through

AE reports and a standard form for excluding participants from further data collection and treatment. Please see **Table 10** below for further details regarding AE reporting.

TABLE 10. Adverse Event Reporting Guidelines

What Event is Reported	When is Event Reported	By Whom	To Whom
Fatal or life-threatening unexpected, suspected serious adverse event	Immediately upon initial receipt of information	Contact PI	
 • IRB of Record • NHLBI • SMC • DCC • All PIs and Co-Is
		Clinical Site PIs	
 • Internal IRBs

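### The printed adverse event questionnaire has no direct item on child self-injury, suicide attempt or harm to others, which the protocol treats as SAEs, so events without medical contact can be missed

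*Combined protocol and SAP*

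**What the plan says.** - **The rule.** Adverse Event Reporting Procedures (addendum approved by the DSMB on 11.18.19) states that "if a child enrolled in the study reports self-injury, a suicide attempt, or harm to others, then this will be addressed as a SAE". The pediatric practice is then told, once study staff learn of the event.
- **The instrument.** Adverse Event Assessment and Tracking explains why both arms complete a form: "To account for differences in the frequency of participant contact between the two study groups", blinded staff use a "standardized questionnaire (see MOP) that is administered at each major assessment time point". Probing depends on a positive answer: "If any items are endorsed on the questionnaire, the blinded measurement staff will gather additional information".
- **The counts.** The same section adds a second tally: "Combining between visit and at visit AEs will result in an alternative count that the DSMB requested". The DCC's monthly report looks for a difference between arms in AE and SAE rates. It does not say which tally it uses.
- **The form.** "Adverse event questionnaires and reporting forms are included in Appendix D of the study protocol". The copy there (PLAN Adverse Event Questionnaire) has 13 yes/no items and a change note dated 5.23.18. For the pandemic, "3 additional questions have been added to the AE questionnaire"; these are not on the printed copy.
- **Administration.** A change dated 10.12.20 says that "Adverse event questionnaires will only be administered after assessment measurement by blinded measurement staff".
- **The stated risk.** Study Halting Rules for Participant Safety lists psychopathology, with disordered eating, among the main risks and says it will be monitored.

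**The concern.** The questionnaire is the plan's means of hearing about adverse events equally in both arms. It can do that only for events that it asks about, or that follow-up of another item brings out. The 11.18.19 rule made three kinds of child event serious whatever their medical consequence, and no documented change to the form followed.

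Two things are at stake:

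- **Comparison.** If the form does not raise these events, they come to light mainly through other contact, and FBT families have far more scheduled contact. A difference between arms that includes between-visit reports could then partly reflect detection. The questionnaire-only count is not tilted in this way, but it can miss the events in both arms.
- **Child safety.** Notification of the pediatric practice starts when staff learn of the event. An event in a UC family that nobody asks about does not start it.

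**Working it through.** The plan gives no figure on this point, so the check sets the event list against the form.

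**1. Inputs.** Events: Adverse Event Reporting Procedures. General SAE definition: Specification of Safety Parameters. Form: Appendix D (13 items), plus three COVID-19 items in Adverse Event Assessment and Tracking. Contacts: Tables 4 and 6. Accrual: the DCVS milestone table.

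**2. Direct items.** 13 + 3 = 16 items. Items that name self-injury, suicide attempt or harm to others: 0.

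**3. Indirect routes.**

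| Event | Items that could lead to it | What remains |
|---|---|---|
| Suicide attempt, medical care received | 1 (overnight hospital stay), 2 (emergency or urgent care), 3 (medical treatment), 7 (new mental health provider) | Likely caught at follow-up |
| Suicide attempt, no care | 12 (anxiety), 13 (low mood), if endorsed and probed | Can be missed |
| Self-injury, care received | 2, 3, 4 (any injury) | Likely caught; intent must come out at follow-up |
| Self-injury, no care | 4 (its examples are a sprain and a fracture; intent is not asked), 12, 13 | Can be missed |
| Harm to others | None naturally; 7 if a counselor was seen | Can be missed |

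The distinct indirect items are 1, 2, 3, 4, 7, 12 and 13, that is 7 of 13.

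**4. Old definition against new rule.** The general definition turns on death, threat to life, hospitalization or lasting disability, and items 1 to 3 suit it. The 11.18.19 rule has no such condition. What it adds, events without medical contact, is what the form reaches least.

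**5. Scheduled contacts over 24 months.** UC: 4 AE surveys. FBT: the same 4 plus the sessions in Table 6 and its note: 4 + 26 = 30, 4 + 48 = 52, 4 + 72 = 76, 4 + 96 = 100. This gives the direction in which detection could differ, not its size.

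**6. Effect of extra SAEs on the stopping guideline.** Table 11 counts intervention-arm SAEs only. Its 20 cells reproduce; for example, with 3 events, n = 41 and p = 0.02, P(X ≥ 3) = 0.0486. At the proposed 2% limit the boundaries for 2, 3, 4 and 5 SAEs are 18, 41, 69 and 99 subjects, so one more SAE moves the boundary by 41 − 18 = 23, 69 − 41 = 28 or 99 − 69 = 30 subjects. Better ascertainment in the FBT arm would therefore feed into it.

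**7. Reach of a late change.** Planned accrual is 56 families in 2017, 336 in 2018 and 82 + 54 = 136 in 2019, in total 528. On 11.18.19 at least 528 − 56 = 472 families (472/528 = 89%) had a 24-month visit ahead. On 12.16.2020, the latest dated approval of an AE change, at least 136 did (136/528 = 26%). Both shares assume accrual to plan. The Randomization section extends enrolment to August 15, 2019, so they may be low.

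**The case against.** **The form in use is not in hand.** The tracking section points to the MOP, and the Appendix D copy predates both the rule and the COVID-19 items. This stands, and it makes the point conditional. Against it, the protocol says that the questionnaires are in Appendix D, and it describes no mental health addition although it records AE changes in 2020.

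**The rule says how to handle a reported event and does not promise to screen for one.** This is correct: no commitment is broken. The gap lies in the questionnaire's stated purpose.

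**Coverage is better than zero direct items suggests.** This stands for medically attended events. Item 4 literally includes any injury, and items 7, 12 and 13 do address psychopathology. A reader might infer that the form cannot detect these events; the table above shows otherwise. Nor can an item put to a parent bring out what the child has told nobody. The gain is in events that the family knows of and staff do not.

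**Unequal contact is already handled.** Both arms get the same blinded form, and calling the pooled tally an alternative suggests that the questionnaire count is the standard one. This is a fair reading, but the monthly report does not say so.

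**The joint wording for parent and child.** A reader might infer that events cannot be attributed. Follow-up and the AE and SAE forms, which are completed per participant, settle whose event it was.

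**Suicidal thoughts.** A reader might want these asked too. The rule does not class them as SAEs, so this point does not extend to them.

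**Conclusion.** The point holds in limited form. The printed questionnaire with its COVID-19 additions has 0 of 16 direct items on three child events that the protocol treats as SAEs. Follow-up of items 1 to 4 and 7 is likely to catch those that received medical care. Mainly untreated self-injury and harm to others can be missed, and outside the questionnaire the FBT arm has many more scheduled occasions on which they can come up.

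A reader might divide the contacts, 30/4 = 7.5 up to 100/4 = 25, and take that as the size of the bias. The documents do not support this. They give no event or detection rates, the UC figure of 4 is a floor because scheduling and retention calls also count as contact, and the ratio is the same with or without a new item. No bias size can be stated.

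The primary analysis and power are unaffected. The imbalance between arms does not enter the stopping guideline, which counts only the intervention arm. Events are probably few, since suicidality and full DSM-5 disorders are excluded at entry.

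The conclusion assumes that the MOP form matches Appendix D plus the COVID-19 items. If the MOP form already has direct items, all that remains is to update Appendix D.

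**What to change.** First check the MOP form. If it lacks the items, add to the questionnaire given by blinded staff in both arms:

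*Since the last visit, has your child (a) hurt himself or herself on purpose, (b) attempted suicide, (c) seriously harmed another person (injury needing care, or school or police action)?* Each part has its own YES/NO.

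The limit in (c) keeps ordinary childhood fights from becoming SAEs. Handle a YES through the existing follow-up, SAE reporting and pediatrician notification, and the suicide and crisis protocols that the protocol already cites. Ask it in person or by call: the remote-assessment script allows the AE survey to be emailed, which does not suit this item.

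State that the between-arm comparison of these events uses the questionnaire-ascertained count, and show the pooled alternative count beside it.

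**Cost.** One short item on a form both arms already complete, through a routine IRB and DSMB amendment. Staff need brief instruction on the crisis pathway, since their described certification covers height, weight and REDCap surveys. A few more SAEs will need reporting and follow-up. Those in the FBT arm enter the Table 11 guideline, so tell the DSMB that ascertainment changed and when. Reach shrinks with delay: on planned accrual, from at least 89% of families with a 24-month visit ahead when the rule was approved to at least 26% by 12.16.2020.
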